individuals assigned to all arms of the CBM-I treatment, as compared to those randomized to complete a series of psychoeducation tutorials, will show a greater increase in positive interpretation bias and a greater reduction in negative interpretation bias and anxiety symptoms from pre-treatment to post-treatment (where post-treatment is measured immediately following session 5). We also expect that treatment gains will be maintained for individuals assigned to CBM-I (vs. psychoeducation) at two-month follow-up. When comparing outcomes within the three CBM-I arms of the study, we expect the high-risk for attrition plus telecoaching group to show greater increases in positive interpretation bias and greater reductions in negative interpretation bias and anxiety symptoms compared to the high risk for attrition group who were not randomized to receive telecoaching. Comparisons between the low risk for attrition group and the high risk for attrition groups (with or without telecoaching) are of secondary interest and these hypotheses are non-directional.

Treatment Dropout Hypotheses

Online mental health interventions have long-been plagued by high user dropout (Eysenbach, 2005). Therefore, it is important to investigate whether adding minimal human contact (i.e., providing telecoaching) to participants identified as being at high risk for treatment dropout improves retention in this online intervention trial. We expect that CBM-I participants identified as being at high risk of treatment dropout who were randomized to receive a supplemental telecoaching intervention will drop out at a later session than high risk CBM-I participants who did not get randomized to the telecoaching intervention. Further, we expect that the three CBM-I arms of the trial will be associated with less attrition than the psychoeducation comparison group.

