criteria listed in the study design section of this registration). Participants were recruited through postings on online newsletters, research websites, mental health forums, Craigslist, social media (e.g., Facebook, Instagram, Twitter, Reddit), and UVA student group listservs; flyers posted in the Charlottesville community and at UVA and other nearby universities and community colleges; news sources (e.g., articles, radio interviews, podcasts); and Google Ads. In addition, to improve recruitment of underrepresented groups, we sent emails to a market research firm's database of participants who self-identified with anxiety or depression and as Black/African American, Hispanic/Latinx, or Asian; we also posted in an online newsletter for multicultural student services at UVA. Note that participants may have presented to the Mindtrails website starting on 3/12/2020 due to concerns over the developing COVID-19 pandemic. Although future analyses may choose to test whether these participants interacted with the intervention differently than did pre-COVID participants, we elect to combine all participants in this initial investigation of the major aims of this clinical trial.

Per protocol, after enrollment and informed consent was obtained, each participant completed a pre-treatment assessment battery, one training session per week over the course of five weeks, comprehensive assessment batteries immediately following training sessions 3 and 5, and a follow-up assessment battery two months after training ended. Participants also completed a shorter schedule of assessments after training sessions 1, 2, and 4 to reduce participant burden.

Participants were compensated via e-gift cards according to the following payment schedule. Participants were awarded \$5 per assessment battery completed at pre-treatment, after session 3, and after session 5. Participants were further awarded \$10 for completing the 2-month follow-up assessment, amounting to a total possible compensation of \$25 in e-gift cards distributed by Tango Cards.

No files selected

Sample Size

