2) Depression, Anxiety, Stress Scales-Short Form - Anxiety Subscale (DASS-AS; adapted from Lovibond & Lovibond, 1995). To assess eligibility to enroll in the study and to measure participants' subjective evaluations of the frequency of their anxiety symptoms since their last training session, participants completed the seven-item DASS-AS using the response scale 0 ("not at all") to 3 ("most of the time"), where higher scores indicate greater symptom severity. Participants also had the option to select Prefer Not to Answer. Participants completed this questionnaire at pre-screener, after session 3, after session 5, and at 2-month follow-up.

No files selected

Indices

No response

No files selected

Analysis Plan

Statistical Models

Models Testing Interpretation Bias and Anxiety Symptom Hypotheses

To assess the impact of different treatment arms on interpretation bias and anxiety symptom outcomes, we will run a series of multilevel models estimated in the Bayesian framework using the rjags package in R. Due to the repeated outcome monitoring structure of this clinical trial, assessment points will be nested within individual participants. We will control for socioeconomic status and age in all models given previous evidence that these demographic characteristics are associated with differential treatment responses to CBM-I. To our knowledge, this will be the first Bayesian test of CBM-I treatment effects and is also the first CBM-I SMART design. As such, we will use uninformative priors in these estimations.

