$$Lvl2 : \beta_{2i} = \gamma_{20} + \gamma_{21}a_1 + \gamma_{22}a_2 + \gamma_{23}Z_{SES} + \gamma_{24}Z_{age} + \gamma_{25}a_1a_2 + \gamma_{26}a_1Z_{SES} + \gamma_{27}a_1Z_{age} + \gamma_{28}a_2Z_{SES} + \gamma_{29}a_2Z_{age} + \gamma_{210}Z_{SES}Z_{age} + \gamma_{211}a_1a_2Z_{SES} + \gamma_{212}a_1a_2Z_{age} + \gamma_{213}a_1Z_{SES}Z_{age} + \gamma_{214}a_2Z_{SES}Z_{age} + \gamma_{215}a_1a_2Z_{SES}Z_{age} + \mu_{2i}$$

$$Lvl2 : \beta_{3i} = \gamma_{30} + \gamma_{31}a_1 + \gamma_{32}a_2 + \gamma_{33}Z_{SES} + \gamma_{34}Z_{age} + \gamma_{35}a_1a_2 + \gamma_{36}a_1Z_{SES} + \gamma_{37}a_1Z_{age} + \gamma_{38}a_2Z_{SES} + \gamma_{39}a_2Z_{age} + \gamma_{310}Z_{SES}Z_{age} + \gamma_{311}a_1a_2Z_{SES} + \gamma_{312}a_1a_2Z_{age} + \gamma_{313}a_1Z_{SES}Z_{age} + \gamma_{314}a_2Z_{SES}Z_{age} + \gamma_{315}a_1a_2Z_{SES}Z_{age} + \mu_{3i}$$

$$Lvl1 : Y_{ij} = \beta_{0i} + \beta_{1i}S_{1j} + \beta_{2i}S_{2j} + \beta_{3i}S_{3j} + e_{ij}$$

Where Y_{ij} is the continuous outcome variable for person i at time j where $i = 1, 2, \dots, N$ and $j = 1, 2, \dots, 7$ (for pre-treatment, session 1, ..., 2-month follow-up); β_{0i} through β_{3i} values are the random effects; S_{1j} is time at the first stage of the clinical trial (pre-treatment to re-randomization point after session 1); S_{2j} is time at the second stage of the clinical trial (session 1 to session 5); S_{3j} is time at the third, or follow-up, stage of the clinical trial (session 5 until two months later); a_1 specifies the treatment arm contrast comparison after the initial randomization; a_2 specifies the treatment arm contrast comparison after re-randomization; Z_{SES} is a control variable for participant socioeconomic status; and Z_{age} is a control variable for participant age.

Note that for simplicity, the above equations only show one a_2 value. Since our four contrasts are not orthogonal, we will attempt to include all four a_2 contrasts in one $rxjags$ model for each outcome variable of interest. If this added complexity prevents model convergence, we will run four separate models, each specifying one of the four a_2 contrast codes.

Estimands. We have identified three estimands of interest upon which to interpret our interpretation bias and anxiety hypotheses: Study arm differences in (1) average outcomes at the end of the session 5 and at 2-month follow-up (i.e., time-specific outcomes); (3) rates of change

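### If DASS-AS used its stated recall window at follow-up, its two-month score averages the whole period since session 5 and does not measure the planned two-month estimand

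*Combined protocol and SAP*

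**What the plan says.** - **Recall window.** Measured Variables, Anxiety Symptoms, item 2, describes DASS-AS as measuring "participants' subjective evaluations of the frequency of their anxiety symptoms since their last training session". The items are frequency ratings from 0 to 3. No other window is given.
- **Administrations.** The same item states: "Participants completed this questionnaire at pre-screener, after session 3, after session 5, and at 2-month follow-up".
- **Timing.** Data Collection Procedures sets a weekly training schedule over five weeks, with the fuller batteries given directly after the third and fifth sessions. The last contact is "a follow-up assessment battery two months after training ended".
- **Hypothesis.** Under Interpretation Bias and Anxiety Hypotheses: "We also expect that treatment gains will be maintained for individuals assigned to CBM-I (vs. psychoeducation) at two-month follow-up".
- **Analysis.** Pre-Registration Table 1 codes follow-up as a single point, with S3 going from 0 at session 5 to 1 at two months. The Estimands paragraph for the interpretation bias and anxiety models lists arm differences in "average outcomes at the end of the session 5 and at 2-month follow-up (i.e., time-specific outcomes". It also lists stage-specific slopes, including session 5 to follow-up, and an area under the curve to follow-up.

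Nothing in the plan adjusts for a window that changes length between visits or limits how the follow-up DASS-AS is interpreted.

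**The concern.** Taken as written, the recall window depends on the visit. It is undefined at the pre-screener. After sessions 3 and 5 it is about one week if the weekly schedule was kept, or close to nothing if the session just completed counts as the last one. At follow-up it is about two months for anyone who finished session 5.

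The follow-up score would then be an average over the post-training interval, used as if it were the level at the end of that interval. Randomization does not remove the problem. Both arms share the window, but the arm difference being measured is the average since session 5 and not the difference at two months. DASS-AS has only one measurement after session 5, so its S3 slope would join two scores with different recall periods.

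What is at stake is the durability claim. A DASS-AS advantage at follow-up could come partly from the early weeks after training and still be reported as an advantage at two months.

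**Working it through.** The plan gives no figure to reproduce, so this is an illustration of size under stated assumptions.

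**Inputs from the plan.** Follow-up two months after training (taken as T = 8.7 weeks); 835 CBM-I and 240 psychoeducation participants in the primary analysis and 559 five-session completers (Sample Size); 95% credible intervals (Inference Criteria).

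**Assumed, not in the plan.** The path of the arm difference after session 5, written as D × f(t) with f(0) = 1 for a fading difference; how respondents weight the weeks they recall; the size of D; and that the session 5 score captures D.

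**Step 1: what the score shows.** With recall weight w(t), the score shows D × ∫f(t)w(t)dt / ∫w(t)dt over 0 to T. Even recall has w = 1. Recency-weighted recall with half-life h has w = 0.5^((T − t)/h).

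For linear fade to zero, f = 1 − t/T:
- Even recall: 0.500.
- Half-life h, with k = ln2/h: [1/k − T·e^(−kT)/(1 − e^(−kT))]/T.
- h = 2 weeks: (2.885 − 0.449)/8.7 = 0.280.
- h = 1 week: (1.443 − 0.021)/8.7 = 0.163.

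| Path of the arm difference | True value at two months | Even recall | 2-week half-life | 1-week half-life |
|---|---|---|---|---|
| Linear fade to zero | 0 | 0.50 D | 0.28 D | 0.16 D |
| Exponential fade, 2-week half-life | 0.05 D | 0.32 D | 0.16 D | 0.09 D |
| Exponential fade, 4-week half-life | 0.22 D | 0.52 D | 0.36 D | 0.29 D |
| Constant | 1.00 D | 1.00 D | 1.00 D | 1.00 D |
| Growing from D to 1.5 D | 1.50 D | 1.25 D | 1.36 D | 1.42 D |

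**Step 2: the S3 slope.** Under linear fade the true change in arm difference is −1.00 D. The scores would show −0.50 D, −0.72 D and −0.84 D in the three recall columns. The loss is attenuated but not hidden.

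**Step 3: area under the curve after session 5** (linear fade, even recall, calendar weeks). The true area is 8.7 × D/2 = 4.35 D. Treating the score as the end of a straight line gives 8.7 × (D + 0.5 D)/2 = 6.53 D. Treating it as the level over the interval gives 8.7 × 0.5 D = 4.35 D.

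**Step 4: chance of a favourable follow-up interval when the true two-month difference is zero.** This is a simple two-group approximation, not the planned Bayesian model. Splitting the 559 completers as the 1075 are split gives 559 × 835/1075 = 434 and 559 × 240/1075 = 125, so SE = √(1/434 + 1/125) = 0.10 SD. The chance is 1 − Φ(1.96 − D × fraction/SE), against 2.5% for a true two-month measure.

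| Assumed D | Even recall | 2-week half-life | 1-week half-life |
|---|---|---|---|
| 0.20 SD | 17% | 8% | 5% |
| 0.35 SD | 41% | 16% | 8% |

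With D = 0.35 and even recall, the figure is 67% if all 835 and 240 are counted, and 29% with 284 and 82 (an assumed 34% retained).

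**The case against.** **The window is not established.** The description is one sentence of purpose covering both screening and outcome measurement, and the questionnaire instruction is not reproduced. The phrase cannot apply at the pre-screener, so it is not the literal instruction at every administration. A reader might infer that the follow-up score definitely covers two months. The documents do not show that. This stands, and it makes the point conditional. It does not remove it, because the only window the plan states does not fit the estimand.

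**The direction is not known.** A reader might assume that the arm difference is largest just after session 5, so that DASS-AS must flatter maintenance. The plan does not say so. Under its own hypothesis of maintained gains, a constant difference gives no distortion, and a growing one would be understated. This stands too.

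**The error rates rest on stacked assumptions.** It is tempting to quote 41% as the false-positive rate. That figure needs even recall and D = 0.35. In Sample Size Rationale, 0.35 belongs to a 2×3 design of delivery platform by CBM-I group that leaves out psychoeducation. No effect size is stated for CBM-I against psychoeducation. The 434/125 split is also assumed, and five-session completers are not the same people as follow-up respondents. Only a range is defensible. Moreover, these are chances of a nonzero follow-up difference, not of concluding that gains were maintained: in the same scenario the slope still shows half the advantage lost.

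**Maintenance does not rest on DASS-AS alone.** OASIS, Recognition Ratings and BBSIQ are also collected at follow-up. This protection is partial. The last two measure interpretation bias, and no recall window is stated for OASIS. For the same reason, and because data collection had already ended, dropping DASS-AS and relying on OASIS would be hard to defend and could look like outcome selection.

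**Conclusion.** The point holds conditionally. If the stated wording was used at follow-up, the DASS-AS arm difference at follow-up and its session 5 to follow-up slope do not measure what the Estimands paragraph defines. With linear fade to zero, the score would show about 16% to 50% of the session 5 difference when none remains, depending on how respondents weight recent weeks. With a constant difference there is no error. For linear fade, the chance of a favourable interval spans about 5% to 41% in the scenarios tabulated, against 2.5%, and it moves further with the number analysed.

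These sizes rest on an 8.7-week window, assumed paths and recall weights, and an assumed D. For participants who stopped before session 5, the window would start at an earlier session. The documents do not support saying that DASS-AS will show gains as maintained after they have gone. They support saying that it could, and that the plan as written neither rules this out nor limits the interpretation.

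**What to change.** 1. Confirm and report the exact DASS-AS recall instruction used at the pre-screener, after sessions 3 and 5, and at follow-up.
2. If follow-up used a fixed window, correct the DASS-AS description under Measured Variables and keep the estimand as it is.
3. If the wording was as described, change the Estimands text:
   - Define the DASS-AS follow-up value as average anxiety from session 5 to follow-up, and report its arm difference under that label.
   - Enter it in the area under the curve as the level over that interval, not as the end point of a line.
   - State that neither this value nor its S3 slope, taken alone, will be interpreted as evidence that gains are maintained at two months.
4. Keep reporting DASS-AS, and read it beside OASIS once the recall wording on the OASIS form has been checked.

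The cost is a check of the forms, revised SAP wording and a small change to one derivation, with no new data. The downside is that DASS-AS gives weaker support for two-month maintenance.

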Further, to code treatment condition for the four treatment arms in line with methods described by Lu and colleagues (2015) and Nahum-Shani and colleagues (2019), we will create a label of contrast codes for each of the two stages of the intervention. We elect to use contrast coding (1/-1) as opposed to dummy coding (0/1) so that we will be able to directly compare outcomes tests of regression coefficients to tests of main effects (see Collins, 2018; Myers, Well, & Lorch, 2010). Because there are two intervention stages by design (i.e., two sequential randomization decision points), we will let (a1, a2) denote the different contrast codes we'll test between treatment arms at both randomization stages.

Let a1 = -1 for participants initially randomized to psychoeducation and let a1 = 1 for participants initially randomized to CBM-I.

Given that there are multiple comparisons of interest following the second randomization point, we specify four different sets of a2 contrast values. These values are delineated in Pre-registration Table 2 such that a2,1 compares the average of all three CBM-I arms to the psychoeducation arm, a2,2 compares the high risk CBM plus telecoaching arm to the high risk CBM with no telecoaching added arm, a2,3 compares the high risk CBM plus telecoaching arm to the low risk CBM arm, and a2,4 compares the high risk CBM with no telecoaching added arm to the low risk CBM arm.

Pre-Registration Table 2

Treatment Arm	a_1	$a_{2,1}$	$a_{2,2}$	$a_{2,3}$	$a_{2,4}$
Low Risk CBM-I Throughout	1	1	0	-1	-1
High Risk CBM-I + Telecoaching	1	1	1	1	0
High Risk CBM-I No Telecoaching Added	1	1	-1	0	1
Psychoeducation throughout	-1	-1	0	0	0

The proposed model equation is provided in Pre-Registration Equation Set 1.

Pre-Registration Equation Set 1

$$Lvl2 : \beta_{0i} = \gamma_{00} + \gamma_{01}Z_{SES} + \gamma_{02}Z_{age} + \gamma_{03}Z_{SES}Z_{age} + \mu_{0i}$$

$$Lvl2 : \beta_{1i} = \gamma_{10} + \gamma_{11}a_1 + \gamma_{12}Z_{SES} + \gamma_{13}Z_{age} + \gamma_{14}a_1Z_{SES} + \gamma_{15}a_1Z_{age} + \gamma_{16}Z_{SES}Z_{age} + \gamma_{17}a_1Z_{SES}Z_{age} + \mu_{1i}$$

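### If the joint model fails, the one-contrast fallback fixes the low-risk slopes at the midpoint of the two high-risk arms, so part of a non-randomized difference can enter the randomized telecoaching estimate

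*Combined protocol and SAP*

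**What the plan says.** The contrasts are set out in Analysis Plan, Statistical Models, Pre-Registration Table 2. Its columns run from a1 through a2,1 to a2,4, and its rows are as follows.

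- The low-risk row is "Low Risk CBM-I Throughout 1 1 0 -1 -1", so this arm has its 0 on a2,2.
- The coached high-risk row is "High Risk CBM-I + Telecoaching 1 1 1 1 0", so this arm has its 0 on a2,4.
- The uncoached high-risk row is "High Risk CBM-I No Telecoaching Added 1 1 -1 0 1", so this arm has its 0 on a2,3.
- The control row is "Psychoeducation throughout -1 -1 0 0 0", so this arm is coded 0 on a2,2, a2,3 and a2,4.

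The text explains that "a2,2 compares the high risk CBM plus telecoaching arm to the high risk CBM with no telecoaching added arm". In Equation Set 1 the S2 and S3 slopes each contain an intercept, a1, a2 and the product a1·a2, plus products with SES and age. There is no separate term for risk group.

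The note under the equations makes a single model with all four contrasts the first choice. It then gives the fallback: "If this added complexity prevents model convergence, we will run four separate models, each specifying one of the four a_2 contrast codes". The same note stands under Equation Set 2 for dropout.

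The Data Exclusion section runs the primary analyses on the 1075 session 1 assessment completers. No sentence restricts a fallback model to the arms that its contrast names.

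The dropout hypothesis is that coached high-risk participants "will drop out at a later session than high risk CBM-I participants who did not get randomized to the telecoaching intervention". The same section says that the high/low-risk comparison does not support causal inference.

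**The concern.** A code of 0 places an arm in a model; it does not take the arm out. With one a2 code per model there are too few arm terms to give each CBM-I arm its own slope, so the third CBM-I arm is tied to the two being compared. When those two carry equal information, the misfit of the third arm cancels out of their difference. When one of them carries more, it does not cancel.

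Telecoaching against no telecoaching is the one contrast among the CBM-I arms that randomization protects. Under the fallback it would depend in part on how low-risk participants fared. The three two-arm models would also disagree with one another: coached minus uncoached, read directly, need not equal the a2,3 result minus the a2,4 result.

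**Working it through.** **1. Counts (Sample Size section).** 282 + 265 = 547; 547 + 288 = 835; 835 + 240 = 1075. The stated analysis set is reproduced.

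**2. Slopes implied by each fallback model.** Write L, T, N, P for low risk, telecoaching, no telecoaching and psychoeducation. For a2,2 to a2,4, a1·a2 equals a2 in every arm, because P is coded 0. In the a2,2 model the S2 slopes are therefore:

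- L = γ20 + γ21
- T = γ20 + γ21 + (γ22 + γ25)
- N = γ20 + γ21 − (γ22 + γ25)
- P = γ20 − γ21

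The S3 slopes have the same form. The constraints are:

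| Model | Constraint |
|---|---|
| a2,1 (identical to a1) | L = T = N |
| a2,2 | L = (T + N)/2 |
| a2,3 | N = (T + L)/2 |
| a2,4 | T = (N + L)/2 |

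P is free in all four, because a1 gives it its own level. The last three constraints hold together only if L = T = N.

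**3. The joint model.** Its arm-level part has 10 columns: intercept, a1, four a2 and four a1·a2. From Table 2, a2,1 = a1 and a2,3 = a2,2 + a2,4. Also a1·a2,1 = 1 in every arm, and the other three products repeat their a2. The rank is 4. The plan uses uninformative priors, so the individual coefficients are not identified, and failure to converge is a realistic outcome.

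**4. Size of the leak, arm-mean form.** Let nT, nN, nL be the information in each arm and ā = (nT − nN)/(nT + nN + nL). With no true telecoaching effect, weighted least squares gives

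spurious T − N = {2·nL·ā / [(nT + nN) − (nT + nN + nL)·ā²]} × (high minus low gap).

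- Equal high-risk arms: 0.
- Stated counts 282/265/288: ā = 17/835 = 0.0204, and 2 × 288 × 0.02036 / (547 − 0.35) = 2.1% of the gap.

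**5. Adding dropout.** The documents give no retention by arm, so it is assumed. Take session 5 retention in the ratio 75 (L) : 60 (P), with T:N at 50:45 or 62:42. Read as percentages, these give

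- 216 + 144 + 141 + 119.25 = 620 completers
- 216 + 144 + 174.84 + 111.3 = 646 completers

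The plan reports 559 five-session completers in the whole ITT set, so 559 is a ceiling. Scaling by 559/620.25 = 0.901 and 559/646.14 = 0.865 gives L/T/N/P of about 68/45/41/54% and 65/54/36/52%. The arm-mean formula depends only on the ratios:

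- 50:45: ā = 21.75/476.25 = 0.0457; leak = 19.73/259.26 = 7.6% of the gap.
- 62:42: ā = 63.54/502.14 = 0.1265; leak = 54.67/278.10 = 19.7% of the gap.

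For a gap of 0.3 to 0.5 SD this is 0.023 to 0.038 SD and 0.059 to 0.098 SD. It counts only session 5 completers. The mixed model also uses early data from those who leave, which shrinks the leak.

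**6. Expected mixed-model estimate.** Generalized least squares with the Table 1 time coding, for the 7-occasion outcome (OASIS) and the 4-occasion outcomes. Assumptions: monotone geometric dropout, baseline variance 1, S2 random-slope variance 0.005 to 0.03, 85% of session 5 completers seen at follow-up, and the plan's common intercept and common CBM-I S1 slope taken as true.

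| High-risk retention ratio | Spurious T − N at session 5 | SE | 95% interval wrongly excludes 0 |
|---|---|---|---|
| 50:45 | 0.02 to 0.03 SD | about 0.08 to 0.12 | about 5 to 7% |
| 62:42 | 0.04 to 0.08 SD | about 0.08 to 0.12 | about 7 to 15% |

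The sign follows the gap. If low-risk participants end lower on anxiety, telecoaching looks slightly worse than it is.

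**7. Consistency.** At 62:42 with a 0.3 SD gap, the a2,2 model gives +0.04 to +0.05, while a2,3 minus a2,4 gives −0.02 for the same quantity. Fitting only the two high-risk arms, or giving every arm its own slopes, returns 0.00 with essentially the same standard error.

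**The case against.** The fallback is conditional, and keeping all arms in it is inferred from silence together with the 1075 set. The text describes each of a2,2 to a2,4 as comparing two named arms, so a reader could take it that only those arms are fitted. That reading is possible, and one sentence would settle it.

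The size is also modest. It needs three things together: the fallback is used, the high-risk arms differ in retention, and the low-risk slope is off the midpoint. The bias stays below one standard error and is at most 0.08/0.35 = 23% of the planning effect of d = .35. With nearly equal high-risk retention the false-exclusion rate is close to nominal. All of this stands and limits the point without removing it.

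Several stronger readings are tempting, and the documents do not support them:

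- *Every arm coded 0 is constrained.* Psychoeducation is coded 0 on three contrasts but is freed by a1.
- *All four fallback models impose a midpoint.* The a2,1 model has no arm coded 0; it forces the three CBM-I arms to be equal.
- *Unequal retention alone causes bias.* If the low-risk slope equals the midpoint, there is none.
- *Dropping the SES and age products would rescue the joint model.* The rank deficiency lies in the arm codes, so it would remain. The plan also gives a reason for interest in these covariates, namely earlier evidence of differential response.
- *The dropout model leaks by a similar amount.* The same constraint applies there, but session completion is itself the outcome and is known for everyone analysed. The unequal-data mechanism does not carry over, and no calculation supports a size.

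**Conclusion.** The point holds for the bias and anxiety outcomes under the fallback as written. The midpoint constraint is algebra from Table 2 and Equation Set 1. Whether it biases the telecoaching estimate depends on a true departure of the low-risk slope from the midpoint and on unequal S2/S3 data in the two high-risk arms. The trial's own retention hypothesis predicts the second. The sizes in the working are illustrations, because arm-specific retention, variances and the 0.3 to 0.5 SD gap are assumptions. A reader might infer that the trial's telecoaching result is in fact biased. The documents do not show that: they do not report that the fallback was used, and they give no outcome by arm. What they show is a stated rule that can bias a randomized contrast, behind a first-choice model that is not identified as coded. The plan should be changed.

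**What to change.** Reword the fallback in one of two ways.

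1. Fit each of a2,2, a2,3 and a2,4 only on the two arms it compares. For a2,2 that is the 547 high-risk participants. Omit a1 and the a1·a2 products, which are redundant within CBM-I.
2. Keep all four arms with a full-rank coding, for example intercept, a1, a2,2 and a2,4 without a1·a2 products, so that each arm has its own S2 and S3 slopes. With coefficients g0, g1, g2, g4 on a slope: L = g0 + g1 − g4, T = g0 + g1 + g2, N = g0 + g1 − g2 + g4, P = g0 − g1. The contrasts follow:
   - T − N = 2·g2 − g4
   - T − L = g2 + g4
   - N − L = 2·g4 − g2
   - mean of the three CBM-I arms minus P = 2·g1

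The second option also cures the non-identification of the joint model and could replace it as first choice. The contrasts must be derived as shown, because the a2,2 coefficient alone is no longer half the telecoaching effect. Use the same coding under Equation Set 2 for consistency.

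The cost is a change of wording and either a data subset or a recoding.
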